#### **7.1.1 Safety Follow-up Evaluation**

Subjects discontinuing from treatment for any reason will have a safety follow-up visit 30 days ( $\pm 7$  days) after the subject receives the last dose of GEN3014 or daratumumab SC. If the subject initiates new anti-cancer treatment within 30 days of the last dose of GEN3014 or daratumumab SC, the safety follow-up visit should be performed prior to starting new anti-

cancer treatment. Once new anti-cancer treatment is initiated, the subject will move into survival status follow-up (see Section 7.1.2).

### **7.1.2 Survival Status**

Survival status will be assessed every 3 months ( $\pm 7$  days), beginning from the day of last GEN3014 or daratumumab SC dose and continuing until the subject dies or withdraws from the trial. Survival status may be requested more frequently around the time of a database lock. Refer to Section 7.3 for guidance regarding subjects lost to follow-up.

Site personnel, or an independent third party, will attempt to collect the survival status of the subject within legal and ethical boundaries for all subjects enrolled. Subjects may be contacted by telephone, email, or visit. Additionally, survival status may be collected through medical records, national registries, or publicly available information as allowed per local regulation. If survival status is determined as deceased, this will be documented.

## **7.2 Subject Discontinuation/Withdrawal from the Trial**

A subject will be withdrawn from the trial for any of the following reasons:

- Death
- Lost to follow-up
- Sponsor decision
- Subject withdraws consent

When a subject withdraws before completing the trial, the reason for withdrawal is to be documented. If the reason for withdrawal from the trial is withdrawal of consent, then no additional assessments are allowed, but the sponsor may retain and continue to use any data collected before the subject withdrew consent.

## **7.3 Lost to Follow Up**

For subjects whose status is unclear because they fail to appear for trial visits without stating an intention to withdraw consent, the investigator should show “due diligence” by contacting the subject, family or family physician as agreed in the ICF and by documenting in the source documents steps taken to contact the subject, eg, dates of telephone calls, registered letters, etc. A subject should not be considered lost to follow-up until due diligence has been completed (as a minimum of 3 documented attempts). Subjects lost to follow-up should be documented.

## 8 TRIAL ASSESSMENTS AND PROCEDURES

### Overview

The Schedule of Activities (see Section 1.3) summarizes the frequency and timing of measurements applicable to this trial. At each visit, trial assessments should be completed before trial drug administration.

Additional serum or urine pregnancy tests may be performed, as determined necessary by the investigator or required by local regulation, to establish the absence of pregnancy at any time during the participation in the trial.

Instructions for the collection, handling, storage, and shipment of samples are found in the laboratory manual that will be provided. Collection, handling, storage, and shipment of samples must be under the specified, and where applicable, controlled temperature conditions as indicated in the laboratory manual.

### 8.1 Demography and Baseline Assessments

#### 8.1.1 Demographics

Demographic details will be assessed at Screening.

#### 8.1.2 Diagnosis and Disease Status

[figure not shown]
The following should be recorded at Screening:

- A subject's history relating to the underlying disease, including primary diagnosis, date of diagnosis, as well as disease status at trial entry, staging, and risk category.
- Cytogenetics and molecular mutational status.
- Transfusion dependency.

Transfusion dependency will be assessed at Screening, every 8 weeks (RRMM and R/R DLBCL) or every 4 weeks (R/R AML) during treatment, and at the end of treatment visit, according to local institution guidelines. The number of units for red blood cells and platelets transfusions must be recorded.

##### 8.1.2.1 RRMM

[figure not shown]
The primary diagnosis of MM, and the status and staging criteria at Screening, will be determined by the IMWG International Staging System (see Section 10.8). The cytogenetic panel for MM used should include, but are not limited to CCI

##### 8.1.2.2 R/R AML

The diagnosis of AML subtype at Screening will be reported according to the WHO 2016 Classification for AML and related neoplasm and risk categorization (Section 10.10).

Molecular mutational status will be done at Screening. CCI

### **8.1.2.3 R/R DLBCL**

The primary diagnosis of DLBCL, and the status and staging criteria at Screening, will be determined by the Ann Arbor staging criteria, including constitutional symptoms (B symptoms), (see Section 10.13).

CCI

### **8.1.3 Medical History**

Any medical condition (signs, symptoms, and diagnosis) or procedures occurring prior to the first dose of GEN3014 or daratumumab SC should be documented in the source documents as medical history. Medical conditions that occur after the ICF is signed and prior to first GEN3014 or daratumumab SC dose should only be reported as AEs if they were assessed by the investigator to be caused by a protocol-mandated procedure (eg, tumor biopsy and/or CT scan).

Any medical history/current medical condition that worsens after the first dose of GEN3014 or daratumumab SC will be documented as an AE. See additional reporting details in Section 8.4 and Section 10.3.

## **8.2 Efficacy Assessments**

Efficacy assessments will be conducted as specified in the Schedules of Activities (Section 1.3). In the Dose Escalation, Expansion Part A (GEN3014 Single Cohorts), and Expansion Part B (Randomized H2H), response to the trial treatment will be reported per the investigator's assessment.

### **8.2.1 Efficacy Assessments for RRMM**

Assessment of tumor response and disease progression will be conducted in accordance with the IMWG Response Criteria (Kumar et al., 2016). Disease evaluations will include measurements of myeloma proteins, bone marrow examinations, skeletal surveys, assessment of extramedullary plasmacytomas, and measurements of  $\beta$ 2-microglobulin, albumin, and serum calcium corrected for albumin. Disease evaluations must be performed every 28 days ( $\pm 3$  days) as defined in Table 1-1 (Dose Escalation), Table 1-5 (Expansion Part A [GEN3014 Single Cohorts]), and Table 1-12 (Expansion Part B [Randomized H2H]) until disease progression according to IMWG Response Criteria (see Section 10.9). All response categories require 2 consecutive assessments made at any time, prior to initiating a new therapy. As minimal residual disease (MRD) will also be evaluated, these criteria will be included per IMWG Response Criteria (Section 10.9); see Section 8.8.3 for more information on assay and methodology.

### **8.2.1.1 Myeloma Protein Measurements in Serum and Urine**

Blood and 24-hour urine samples for M-protein measurements will be sent to and analyzed by a central laboratory. The investigator will use results provided by the central laboratory for disease assessment. Only 1 serum and one 24-hour urine sample per time point are required by the central laboratory to perform the following tests.

- Serum quantitative Ig panel: IgG, IgA, IgM, IgE, and IgD at Screening as indicated on [Table 1-1](#) (Dose Escalation), [Table 1-5](#) (Expansion Part A [GEN3014 Single Cohorts]), and [Table 1-12](#) (Expansion Part B [Randomized H2H]). These analyses will be performed by the local laboratory.
- Serum M-protein quantitation by electrophoresis (SPEP).
- Serum immunofixation (IFE) at Screening and thereafter when M-protein is non-quantifiable.
- Serum FLC assay.
- 24-hour urine M-protein quantitation by electrophoresis (UPEP).
- Urine IFE at Screening and thereafter when a M-protein is non-quantifiable.

Blood and 24-hour urine samples will be collected as specified in [Table 1-1](#) (Dose Escalation), [Table 1-5](#) (Expansion Part A [GEN3014 Single Cohorts]), or [Table 1-12](#) (Expansion Part B [Randomized H2H]) until disease progression. Disease progression based on 1 of the laboratory tests alone must be confirmed by a repeat sample testing 1 to 4 weeks later. Serum and urine IFE will be performed at Screening and at the time when a CR is suspected (when serum or 24-hour urine M-protein electrophoresis [by SPEP or UPEP] are 0 or non-quantifiable). For subjects with light chain MM, serum IFE test, urine IFE test, and serum FLC assay will be performed routinely.

Both GEN3014 and daratumumab may be detected on SPEP and serum IFE assays which leads to false positive SPEP and serum IFE assay results in subjects with IgG1κ myeloma protein and therefore affects assessments of responses. For subjects who have achieved a very good partial response (VGPR) or better with suspected GEN3014 or daratumumab interference, a GEN3014-specific or daratumumab-specific IFE assay **CCI** XXXXXXXXXX will be performed at the central laboratory. Subjects who meet all other IMWG criteria for CR/stringent complete response (sCR) (see Section 10.9), and whose positive IFE indicates interference from GEN3014 or daratumumab, will be considered complete responders.

### **8.2.1.2 Serum Calcium Corrected for Albumin**

Blood samples for calculating serum calcium corrected for albumin will be collected and analyzed locally, as specified in [Table 1-1](#) (Dose Escalation), [Table 1-5](#) (Expansion Part A [GEN3014 Single Cohorts]), or [Table 1-12](#) (Expansion Part B [Randomized H2H]) until disease progression. Development of hypercalcemia (corrected serum calcium >11 mg/dL [ $>2.75$  mmol/L]) can indicate disease progression or relapse if it is not attributable to any other cause (see IMWG disease response criteria in Section 10.9). Calcium binds to albumin and only the unbound (free) calcium is biologically active; therefore, the serum calcium level must be adjusted for abnormal albumin levels ("corrected serum calcium"). The formula for adjustment is presented in Section 10.7. Measurement of free ionized calcium is an acceptable alternative to corrected serum calcium for determining hypercalcemia. Free ionized calcium levels greater than the ULN are considered to be hypercalcemic for this trial.

### **8.2.1.3 Bone Marrow Examination**

Bone marrow aspirate and/or biopsy will be performed for clinical assessments and biomarker evaluations.

At Screening, clinical characterization of the myeloma (morphology, cytogenetics, and IHC or immunofluorescence or flow cytometry) may be done by a local laboratory and a portion of the bone marrow aspirate is required to be sent to the central laboratory to establish baseline MM clonality to monitor MRD and to perform biomarker analyses as described in Section 8.8.1 and Table 1-1 (Dose Escalation), Table 1-5 (Expansion Part A [GEN3014 Single Cohorts]), and Table 1-12 (Expansion Part B [Randomized H2H]). In addition, non-decalcified diagnostic slides (bone marrow aspirate, touch preparation or clot selection) or formalin-fixed paraffin-embedded (FFPE) block (clot section only, no bone marrow biopsy) up to 42 days prior to enrollment may be collected for MRD assessment.

Bone marrow assessment for diagnosis and response will be performed at a local laboratory. Both bone marrow aspirate and bone marrow biopsy are required at Screening. Additional bone marrow aspirate and/or bone marrow biopsy collections will be performed during GEN3014 or daratumumab treatment to confirm CR/sCR or relapse from CR/sCR, as clinically indicated. In addition, MRD may be evaluated for subjects who achieve CR at time points as detailed in Section 8.8.3 and Table 1-4 (Dose Escalation), Table 1-9 (Expansion Part A [GEN3014 Single Cohorts]) and Table 1-15 (Expansion Part B [Randomized H2H]). For sCR IHC immunofluorescence requires kappa/lambda ratio analysis of  $\geq 100$  cells or 2- to 4-color flow cytometry.

First or second pulls for all collections are strongly preferred.

Additional biomarker evaluations are described in Section 8.8.1.

### **8.2.1.4 Extramedullary Plasmacytomas**

Sites of known extramedullary plasmacytomas must be documented during the Screening period. PET/CT is the preferred imaging modality for extramedullary sites of disease. MRI or clinical examination can be used to document extramedullary sites of disease. CT scan evaluation is an acceptable alternative (if no contraindication to use of IV contrast). PET scans and ultrasound are not acceptable methods for documentation of size of extramedullary plasmacytomas.

For all subjects with a history of plasmacytomas or if clinically indicated, an assessment of extramedullary plasmacytomas must be performed at Screening by clinical examination or radiologic imaging. Assessments of plasmacytomas can be done locally every 4 weeks by physical examination. For subjects with a history or subjects, as clinically indicated during treatment, assessments of plasmacytomas are performed until development of confirmed CR or confirmed PD.

If assessment can be done radiologically, then evaluations may be done every 12 weeks. Methodology of assessments must be consistent throughout all visits. Irradiated or excised lesions will be considered not measurable, and will only be monitored for PD.

To qualify for PR or MR, in addition to meeting the criteria set for M protein or FLC levels or percent of plasma cells, if present at baseline, a  $\geq 50\%$  reduction in the sum of the products of the maximal perpendicular diameters (sum of the product of the diameters [SPD]) of soft tissue plasmacytomas is also required. PD per plasmacytomas includes the appearance of a new lesion(s),  $\geq 50\%$  increase from nadir in SPD of  $>1$  lesion, or a  $\geq 50\%$  increase in the longest

diameter of a previous lesion in >1 cm short axis. (See IMWG 2016 disease progression criteria in Section 10.9).

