Bone marrow aspirate  and/or bone marrow biopsy	8.2.1.3	Assess disease at baseline, confirm CR/sCR, assess MRD, and for other biomarker evaluations (see Table 1-13 and Table 1-14 )	X 	Collect at time of suspected CR/sCR. Also collect at 6, 12, 18, 24 and 30 (±1) months post C1D1 for subjects who achieve CR/sCR and remain on trial. At investigator's discretion, may be repeated if clinically indicated. 								X	X 		
Assess extramedullary plasmacytomas 	8.2.1.4	Subject with history of plasmacytomas, or if clinically indicated at Screening.	X 	Measure every 4 weeks for physical examination (if applicable) and every 12 weeks for imaging assessment 								X			
Response Assessment	8.2.1	To be performed starting C2D1		X (C2)					X		X	X	X		
END OF TREATMENT															
New anti-cancer	7.1.1													X	X

Cycle(s)	Pro- tocol Section	Notes	Screen- ing	Q1W (Weekly)					Q2W		Q4W	UNS	End of Treat- ment	Safety Follow- up 	Survival Status/ contact 
				Cycles 1-2					Cycles 3-6		Cycle 7 onward				
Cycle Day			D -21 to D -1	D1 	D2 (C1 only, GEN- 3014)	D8	D15	D22	D1	D15	D1		ASAP after last dose	30d after last dose	Q3M
Visit Window							±3d		±3d		±3d		+7d	+7d	±7d
therapy															
Survival Status	7.1.2														X

ADA=anti-drug antibody; AE=adverse event; ASAP=as soon as possible; C=cycle; CMV=cytomegalovirus; CR=complete remission; CT=computed tomography; CCI=central laboratory; D/d=day; ECG=electrocardiogram; ECOG PS=Eastern Cooperative Oncology Group performance status; FFPE=formalin-fixed, paraffin-embedded; FLC=free light chain; h=hour(s); HBV=hepatitis B virus; HCV=hepatitis C virus; HIV=human immunodeficiency virus; ICF=informed consent form; Ig=immunoglobulin; IRR=infusion-related reaction; min=minute(s); MM=multiple myeloma; MRD=minimal residual disease; MRI=magnetic resonance imaging; PD=progressive disease; PK=pharmacokinetic(s); Q3M=every 3 months; Q1W=every week; Q2W=every 2 weeks; Q4W=every 4 weeks; RRMM=relapsed or refractory multiple myeloma; SAE=serious adverse event; sCR=stringent complete response; SPEP=serum protein electrophoresis; TLS=tumor lysis syndrome; UNS=unscheduled; UPEP=urine protein electrophoresis.

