- SPEP, UPEP, serum FLC, serum IFE, and urine IFE should be performed preferably within 14 days prior to C1D1 (during Screening), and on C1D1. Subsequent on-treatment SPEP and UPEP are to be performed every 28 (±3) days on the scheduled assessment day. All responses based on biochemical investigations, including PD, require 2 consecutive assessments by central lab for confirmation. Once PD is confirmed, subsequent disease assessments are not required. Additional aliquots will be collected for IFE reflex testing, in case of potential interference of GEN3014 or daratumumab with interpretation of M-protein levels.
- Perform serum FLC and serum/urine IFE at Screening and when CR is suspected or maintained. Perform serum FLC on Day 1 of every cycle for all subjects.
- A skeletal survey, including cranium, is required during Screening. Results from skeletal survey performed within 42 days before C1D1 as routine follow up for subject's disease state may be used. Additional imaging will be performed as clinically indicated.

11. At Screening, fresh bone marrow aspirate and biopsy are required for clinical assessment of disease. At baseline (Screening) only, non-decalcified diagnostic slides (bone marrow aspirate, touch preparation or clot selection) or FFPE block (clot section only, no bone marrow biopsy) up to 42 days prior to enrollment may be collected for MRD assessment if the fresh aspirate fails to calibrate during testing.
12. Bone marrow aspirate and/or biopsy will be conducted locally to confirm CR/sCR. A portion of bone marrow aspirate will be sent to central laboratory to confirm CR/sCR, assess MRD (at time of suspected CR/sCR, and at 6, 12, 18, 24, and 30 [ $\pm$ 1] months post C1D1 for subjects who achieve CR/sCR and remain on trial), and for other biomarker evaluations. If 1 of the time points for collection to assess MRD occurs within 1 month of suspected CR, a repeat bone marrow will not be requested. The bone marrow tests at CR/sCR and beyond will only be required if subject's response is near CR or better by blood and urine evaluations. If clinically feasible, a bone marrow aspirate will also be performed at End of Treatment/PD.

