## 10.9 Appendix 9: 2016 International Myeloma Working Group (IMWG) Uniform Response Criteria for Response and Minimal Residual Disease Assessment in Multiple Myeloma

IMWG criteria for response assessment including criteria for MRD 	
Response Subcategory	Response Criteria
IMWG MRD criteria (requires a complete response as defined below)	
Sustained MRD-negative	MRD negativity in the marrow (NGF, NGS, or both) and by imaging as defined below, confirmed minimum of 1 year apart. Subsequent evaluations can be used to further specify the duration of negativity (eg, MRD-negative at 5 years) 
Flow MRD-negative	Absence of phenotypically aberrant clonal plasma cells by NGF  on bone marrow aspirates using the EuroFlow standard operation procedure for MRD detection in MM (or validated equivalent method) with a minimum sensitivity of 1 in 10  nucleated cells or higher
Sequencing MRD-negative	Absence of clonal plasma cells by NGS or bone marrow aspirate in which presence of a clone is defined as less than 2 identical sequencing reads obtained after DNA sequencing of bone marrow aspirates using the LymphoSIGHT platform (or validated equivalent method) with a minimum sensitivity of 1 in 10  nucleated cells  or higher
Imaging plus MRD-negative	MRD negativity as defined by NGF or NGS plus disappearance of every area of increased tracer uptake found at baseline or a preceding PET/CT or decrease to less mediastinal blood pool SUV or decrease to less than that of surrounding normal tissue 
Standard IMWG response criteria 	
sCR	Complete response as defined below plus normal FLC ratio  and absence of clonal cells in bone marrow biopsy by IHC ( $\kappa/\lambda$ ratio $\leq 4:1$ or $\geq 1:2$ for $\kappa$ and $\lambda$ patients, respectively, after counting $\geq 100$ plasma cells 
CR	Negative IFE on the serum and urine and disappearance of any soft tissue plasmacytomas and $\leq 5\%$ plasma cells in bone marrow aspirates
VGPR	Serum and urine M-protein detectable by IFE but not on electrophoresis or $\geq 90\%$ reduction in serum M-protein plus urine M-protein level $< 100$ mg per 24 h

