PD	
Any 1 or more of the following criteria:
 
Increase of <math>\geq 25\%</math> from lowest confirmed response value in 1 or more of the following criteria:
 
 
Serum M-protein (absolute increase must be <math>\geq 0.5</math> g/dL);
 
Serum M-protein increase <math>\geq 1</math> g/dL, if the lowest M component was <math>\geq 5</math> g/dL;
 
Urine M-protein (absolute increase must be <math>\geq 200</math> mg/24 hr).
 
In patients without measurable serum and urine M-protein levels, the difference between involved and uninvolved FLC levels (absolute increase must be <math>>10</math> mg/dL);
 
In patients without measurable serum and urine M-protein levels and without measurable involved FLC levels, bone marrow plasma-cell percentage irrespective of baseline status (absolute increase must be <math>\geq 10\%</math>);
 
Appearance of a new lesion(s), <math>\geq 50\%</math> increase from nadir in SPD of <math>>1</math> lesion, or <math>\geq 50\%</math> increase in the longest diameter of the previous lesion <math>>1</math> cm in short axis;
 
<math>\geq 50\%</math> increase in circulating plasma cells (minimum of 200 cells per <math>\mu\text{L}</math>) if this is the only measure of disease
 

Clinical Relapse	
Clinical relapse requires 1 or more of the following:
 
 
Direct indicators of increasing disease and/or end organ dysfunction (CRAB features) related to the underlying clonal plasma-cell proliferative disorder. It is not used in calculation of time to progression or PFS but is listed here as something that can be reported optionally or for use in clinical practice;
 
Development of new soft tissue plasmacytomas or bone lesions (osteoporotic fractures do not constitute progression);
 
Definite increase in the size of existing plasmacytomas or bone lesions. A definite increase is defined as a 50% (and <math>\geq 1</math> cm) increase as measured serially by the SPD10 of the measurable lesion;
 
Hypercalcemia (<math>>11</math> mg/dL)
 
Decrease in hemoglobin of <math>\geq 2</math> g/dL, not related to therapy or other non-myeloma related conditions;
 
Rise in serum creatinine by 2 mg/dL or more from the start of therapy and attributable to myeloma;
 
Hyperviscosity related to serum paraprotein
 

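### Protocol Section 8.2.1.4 ends plasmacytoma assessment at confirmed CR, whereas Section 8.2.1 carries it to progression; in a few subjects an extramedullary relapse after CR may be found late or not documented as PD

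*Protocol*

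**What the plan says.** Three places in the protocol govern how long plasmacytomas are followed in RRMM.

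- Section 8.2.1.4, for subjects with a history or a clinical indication: "assessments of plasmacytomas are performed until development of confirmed CR or confirmed PD".
- Section 8.2.1: "Disease evaluations will include measurements of myeloma proteins, bone marrow examinations, skeletal surveys, assessment of extramedullary plasmacytomas", among other items, to be done every 28 days "until disease progression according to IMWG Response Criteria".
- The plasmacytoma row of Table 1-12, with the same rhythm in Tables 1-1 and 1-5: "Measure every 4 weeks for physical examination (if applicable) and every 12 weeks for imaging assessment". The row applies to "Subject with history of plasmacytomas, or if clinically indicated at Screening". It gives no end point, neither CR nor PD. The only stop for disease assessments in the table footnotes, attached to the M-protein rows, is "Once PD is confirmed, subsequent disease assessments are not required".

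Appendix 9 (Section 10.9) defines CR as including "disappearance of any soft tissue plasmacytomas" and makes a new lesion sufficient for PD by itself. Its note 11 says that, for time to progression and PFS, subjects who have reached CR and are MRD-negative are still judged by the PD criteria.

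DOR and PFS (Protocol Sections 9.4.3.2 and 9.4.3.4; SAP Sections 5.4.3 and 5.4.5) run to progression or death, with no stop at CR.

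**The concern.** Sections 8.2.1 and 8.2.1.4 give sites different instructions for the same assessment. A site that follows 8.2.1.4 stops scheduled looking for plasmacytomas once CR is confirmed; a site that follows 8.2.1 continues. The trial is open-label with investigator-assessed response, so how closely progression is ascertained after CR could depend on which section a site applies.

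The stop at CR also does not fit the endpoints. A new lesion is a PD event, and DOR and PFS count PD events after CR. Ending the scheduled check at CR removes the planned source of that component in subjects selected for it because of history or clinical indication. If disease returns first outside the marrow without a biochemical signal, progression may be dated late or not documented. Either error lengthens DOR and PFS.

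**Working it through.** The documents state no event count, power or expected size for DOR or PFS, so there is no plan figure to reproduce. The check is a comparison of text, followed by an illustration on assumed rates.

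**Stop rules side by side**

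| Component | Place in protocol | End of assessment |
|---|---|---|
| All RRMM disease evaluations | 8.2.1 | Progression |
| Serum and urine M-protein | 8.2.1.1 | Progression |
| Corrected calcium | 8.2.1.2 | Progression |
| Plasmacytomas | 8.2.1.4 | Confirmed CR or confirmed PD |
| Skeletal imaging on treatment | 8.2.1.5 | When clinically indicated, before PD is confirmed |
| Plasmacytoma row | Tables 1-1, 1-5, 1-12 | None stated |

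Among these, plasmacytoma assessment is the only one with a stop at CR.

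**Whether biochemistry covers the gap.** Only in part. Under Appendix 9 a positive immunofixation alone after CR is not progression, and PD by serum M-protein needs an absolute rise of at least 0.5 g/dL. The lesion criterion is a separate route to PD.

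**What the SAP does with such a relapse.** Table 8 counts documented PD or death as the event. Clinical progression recorded in the eCRF without documented PD leads to censoring. The last valid assessment excludes only time points rated not evaluable. A CR time point at which plasmacytomas were not examined could therefore count as valid.

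**Illustration per Part B arm.** Only n = 40 (Protocol Section 4.1.4) is from the documents. The three rates are assumptions, and CR and plasmacytoma follow-up are treated as independent.

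- c = share reaching CR or better: 0.05 to 0.20
- h = share under plasmacytoma follow-up: 0.05 to 0.20
- r = share of those relapsing first outside the marrow without a biochemical signal: 0.10 to 0.50

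Subjects in CR whose scheduled assessment would stop, n × c × h:

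- low: 40 × 0.05 × 0.05 = 0.1
- high: 40 × 0.20 × 0.20 = 1.6

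Chance of at least one such subject in an arm, 1 − (1 − c × h)^40:

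- low: 1 − 0.9975^40 = 9.5%
- high: 1 − 0.96^40 = 80.5%

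Late or undocumented PD events, n × c × h × r:

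- low: 0.1 × 0.10 = 0.01
- high: 1.6 × 0.50 = 0.8

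**The case against.** Section 8.2.1 is a general sentence and cannot be literal for every item it lists. Beta-2 microglobulin is measured at Screening only, skeletal imaging after Screening is driven by clinical indication, and plasmacytoma imaging is 12-weekly, not 28-daily. On that view 8.2.1.4 is the specific rule and prevails. The stop has some logic too: CR requires plasmacytomas to have gone, so nothing is left to measure. The documents do not show that it was an oversight.

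Detection also does not cease at CR. M-protein testing every 28 days, serum FLC on Day 1 of each cycle, cycle-wise response assessment, symptom-directed examination, unscheduled plasmacytoma assessment and symptom-driven CT or X-ray all continue. PD documented by any of these is an event.

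Much of this stands, and it limits what can be said. A reader might infer that the schedules expressly carry plasmacytoma assessment to progression; their rows state no end point. A reader might infer that extramedullary relapse after CR is simply missed; at most, one that is biochemically silent may be found late or go undocumented. Nor does an affected subject necessarily remain progression-free on paper until the M-protein rises or death occurs, because clinical progression without documented PD, and new anti-cancer therapy, lead to censoring.

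The objection does not remove the inconsistency. Items with their own rhythm can still share one end point, and having no lesion left to measure does not answer the criterion of a new lesion, which applies after CR.

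**Conclusion.** The inconsistency is real: 8.2.1.4 stops at confirmed CR, 8.2.1 does not, and the schedule rows are silent on an end point. Followed as written, 8.2.1.4 ends scheduled checking of one PD component while DOR and PFS are still running.

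The consequence is small and conditional. It is confined to subjects with a plasmacytoma history or indication who reach confirmed CR and then relapse first outside the marrow without a biochemical signal. The direction is towards longer DOR and PFS, and the size is under one event per arm throughout the assumed range. ORR is untouched because the stop comes after the response. DOR and PFS are secondary and descriptive, with no hypothesis test.

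Two further inferences are not supported. A bias between the Part B arms would need unequal numbers of affected subjects, for example through unequal CR rates, which the documents do not give. Duration of CR is not a listed endpoint, so nothing can be said to be biased there. This is a minor correction, worth making because it is cheap.

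**What to change.** In Protocol Section 8.2.1.4, delete the reference to confirmed CR from the stop rule, so that plasmacytoma assessment runs until confirmed PD. Adding the same end point to the plasmacytoma rows of Tables 1-1, 1-5 and 1-12 would make the three places agree explicitly.

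It would also help to state in the SAP, next to Table 8, whether a time point without plasmacytoma assessment counts as a valid assessment for DOR and PFS in these subjects.

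The text change is three words in 8.2.1.4 and optional lines elsewhere. The practical cost is continued 4-weekly examination or 12-weekly imaging for subjects in CR with a plasmacytoma history or indication: 0.1 to 1.6 subjects per Part B arm on the assumed rates. Section 8.2.1 already asks for this follow-up, so no new assessment is introduced.
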